**Instruments:**

Name	Concept measured	Number of items
QOL-MV	Quality of life in mechanically ventilated patients questionnaire	12
SIT	Sentence intelligibility test	11
SOFA	Sequential Organ Failure Assessment Tool	6
Additional questions	Demographic Data	

**Study Protocol**

Date: 2/06/18

Principal Investigator: [name]

Application Number: **IRB00080981**

- b. Study duration and number of study visits required of research participants.

The study duration is estimated to be 4 weeks per patient with a total of 3 visits by the study team.

- c. Blinding, including justification for blinding or not blinding the trial, if applicable.

Patients will not be blinded to intervention or control group.

- d. Justification of why participants will not receive routine care or will have current therapy stopped.

If patient is not willing to participate in the study, their routine care will not be altered. Participants in the control group will receive routine care, and participants in the intervention group will initiate the same intervention as routine care with timing to be 24-60 hours earlier than the current routine care.

- e. Justification for inclusion of a placebo or non-treatment group.

N/A

- f. Definition of treatment failure or participant removal criteria.

If there is a change in clinical condition that prevents study team from continuing with OWSV trial or if the patient is discharged from the hospital, the patient will be removed from the study.

- g. Description of what happens to participants receiving therapy when study ends or if a participant's participation in the study ends prematurely.

If participants receiving the OWSV complete the study (after Session 3), they will continue to use the OWSV per our current standard of care. If the participant's participation using the OWSV ends prematurely due to change in clinical condition, then they will be dropped from the study. But if their condition improves and warrants reuse of the OWSV, they will be offered the OWSV per our standards of care but will not be re-enrolled in the study.

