**Sequence and timing:**

- A. Screening by Tracheostomy Nurse Practitioner following percutaneous tracheotomy
1. Glasgow Coma Scale (GCS)
  2. Richmond Agitation Sedation Scale (RASS)
- B. Speech-Language Pathologist consult is placed for patients meeting study inclusion criteria
- C. Patient consent is obtained by Tracheostomy Nurse Practitioner or Speech-Language Pathologist
- D. Randomization into Intervention and Control groups
- E. Session 1 within 12-24 hours following percutaneous tracheotomy:
1. Both groups complete pre-assessment consisting of the following:
    - i. Electronic Patient Records (POE, EPR, or EPIC)
      1. Demographic Data
      2. Patient Characteristics
      3. Sequential Organ Failure Assessment (SOFA)
    - ii. Confusion Assessment Method for the ICU (CAM-ICU)
    - iii. Health-related quality of life survey, Quality of Life – Mechanical Ventilation (QOL-MV)
    - iv. Tracheostomy-related assessment
      1. Trach size
      2. Mechanical ventilation status
      3. Secretions & tolerance of cuff deflation
      4. Presence of complications
        - i. Bleeding at stoma
        - ii. Subcutaneous air
        - iii. Infection at stomal site
        - iv. Pneumothorax
        - v. Accidental decannulation
  2. Intervention Group completes standard SLP evaluation and OWSV trial:
    - i. SLP evaluation includes the following to assess candidacy for OWSV trial:
      1. Level of alertness
      2. Cranial nerve exam
      3. Ability to cough
      4. Ability to tolerate cuff deflation
      5. Ability to tolerate finger occlusion
      6. Vocal quality
    - ii. If appropriate, OWSV will be trialed and assessed for the following:
      1. Duration of tolerance
      2. Change in vital signs
      3. Vocal quality
      4. Presence of air trapping
      5. Sentence Intelligibility Test
    - iii. Recommendations are made for OWSV use outside of SLP supervision
      1. Supervision requirement (RN, Respiratory therapist, trained family, independent)
      2. Duration of OWSV use
  3. Control Group receives no further evaluation or treatment during Session 1, which constitutes current standard of care.
- F. Session 2 within 48-60 hours following percutaneous tracheotomy:
1. Both groups complete post-assessment:

Date: 2/06/18

Principal Investigator: [name]

Application Number: IRB00080981

[figure not shown]
- i. Electronic Patient Records (POE, EPR, or EPIC)
    1. Demographic Data
    2. Patient Characteristics

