## 7. Study Statistics

- a. Primary outcome variable.

Speech intelligibility

- b. Secondary outcome variables.

- Patient characteristics
- Quality of Life
- Complications
- Time to events
- Length of stay
- Mortality

\*See codebook for list of additional variables

- c. Statistical plan including sample size justification and interim data analysis.

Mean, standard deviation, median and inter-quartile range will be calculated for continuous variables. Paired t-tests will be used to compare pre and post assessment scores for continuous variables. Frequencies and percentages will be calculated for categorical variables. Chi square and Fisher Exact tests will be used to compare pre and post assessment scores of categorical variables. Sample size is estimated based on 30% of tracheostomy patients who might be awake and interactive at the Johns Hopkins Hospital in 2016, as per the tracheostomy database. According to the 2014 data, we found that about 55 patients were awake and interactive while having a percutaneous tracheostomy tube at the hospital. Considering a 10% of the patients who may not be interested in the study, we will plan for a sample size of 50 with 25 in the intervention group and 25 in the control group.

- d. Early stopping rules.

If patients have changes in clinical condition that prevents cuff deflation, they will be dropped from the study. The study will be halted if any major complications occur from early trial of OWSV.

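### Sections 4f, 4g and 7d take randomised patients out of the study, not only off the valve, so complications after early OWSV can go uncounted before Session 2 and bias Hypothesis 3b

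*Combined protocol and SAP*

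**What the plan says.** Consent and randomisation (section 4a, steps C and D) come before Session 1, so every later removal is a post-randomisation exclusion. Three places set the rules:

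- Section 4f: if a clinical change stops the team "from continuing with OWSV trial or if the patient is discharged from the hospital, the patient will be removed from the study".
- Section 4g: "If the participant's participation using the OWSV ends prematurely due to change in clinical condition, then they will be dropped from the study". If such patients recover, they "will be offered the OWSV per our standards of care but will not be re-enrolled in the study".
- Section 7d: "If patients have changes in clinical condition that prevents cuff deflation, they will be dropped from the study". The same section adds a study-level rule: "The study will be halted if any major complications occur from early trial of OWSV".

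Section 8b says that valve trials are discontinued if a complication occurs, and deferred if the patient is not a suitable candidate. It does not say whether either patient stays in the study.

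In the schedule (section 4a), Session 1 at 12-24 hours opens with "Both groups complete pre-assessment consisting of the following". The list that follows includes five complications: stomal bleeding, subcutaneous air, stomal infection, pneumothorax and accidental decannulation. The intervention arm's valve trial is listed after it. For controls, "Control Group receives no further evaluation or treatment during Session 1, which constitutes current standard of care". Session 2 at 48-60 hours repeats the complication list in the post-assessment of both arms, followed by the valve trials, which are the controls' first. Session 3 lists no complication assessment. Section 4b states: "The study duration is estimated to be 4 weeks per patient with a total of 3 visits by the study team".

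Section 7c names descriptive statistics and pre/post tests. It gives no analysis set and no rule for removed patients.

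**The concern.** The abstract gives the trial's purpose as investigating the safety of early OWSV use, and Hypothesis 3b predicts no significant difference in complications. A complication can itself be the clinical change that ends valve use. Removal can therefore depend on the outcome being compared, and can do so before the only scheduled use of the complication list after early valve exposure.

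If patients with complications are removed more often than patients without, and more so in the intervention arm, the comparison moves towards the predicted result or towards early OWSV. The same rules can leave ICU stay and mortality incomplete. They could also affect the quality-of-life change in Hypothesis 3a, if those removed would have scored differently at Session 2.

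**Working it through.** **The plan's own figure.** Section 7c starts from about 55 eligible patients and allows 10% for those not interested: 55 × 0.90 = 49.5, planned as 50 (25 per arm). This reproduces. The 10% covers refusal, so nothing is allowed for removal after randomisation.

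**Which rule reaches which arm before Session 2.**

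- Rules tied to continuing or using the valve (4f, 4g): mainly intervention patients, since controls are not scheduled for a valve trial until after the Session 2 post-assessment.
- Cuff deflation (7d) and discharge (4f): both arms.

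**Where a complication can be lost.** At Session 2 the complication list comes before the valve trial, so a complication that stops that trial should already have been recorded. Loss needs removal between the two sessions, or a Session 2 that is not held. Session 1 can end with a recommendation for valve use outside SLP supervision, so valve exposure between visits is foreseen.

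**Size, on assumed rates.** The documents give no complication or removal rates. Let p be the true complication rate, f the fraction removed among patients with a complication, and g the fraction removed among those without. Removed patients are taken as uncounted.

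Observed rate = p(1−f) / [p(1−f) + (1−p)(1−g)]

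Observed odds ratio = true odds ratio × (1−fI)(1−gC) / [(1−fC)(1−gI)], where I is intervention and C is control.

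Take a true 20% v 10% (odds ratio 2.25), with no control removals and no uncomplicated patient removed (fC = gI = gC = 0):

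| fI | Intervention arm shows | Control arm shows | Difference (points) | Odds ratio |
|---|---|---|---|---|
| 0 | 20.0% | 10.0% | 10.0 | 2.25 |
| 10% | 0.18/0.98 = 18.4% | 10.0% | 8.4 | 2.25 × 0.90 = 2.03 |
| 25% | 0.15/0.95 = 15.8% | 10.0% | 5.8 | 2.25 × 0.75 = 1.69 |
| 50% | 0.10/0.90 = 11.1% | 10.0% | 1.1 | 2.25 × 0.50 = 1.13 |

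In whole patients, 5/25 (20.0%) becomes 4/24 (16.7%) after one such removal and 3/23 (13.0%) after two.

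**Sensitivity to g.** With true rates equal at 20%, fI = 50% and no control removals, the odds ratio is 0.50 at gI = 0, 0.50/0.75 = 0.67 at gI = 25%, and 1.0 at gI = 50%. If gI exceeds fI, the bias reverses.

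**Power.** For a two-sided Fisher test between arms at 0.05 with 25 per arm, a true 20% v 10% has power 8.6% with no removal, 8.0% with fI = 10% and 2.4% with fI = 50%. For 40% v 10%, power falls from 59% to 20% at fI = 50%. Section 7c names Fisher's test only for pre/post comparison, so these figures describe a test that the plan does not specify.

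**The case against.** The strongest reply is that the route to loss is narrow. Complications are listed before the valve trial at Session 2, air trapping and vital signs are assessed during the valve trial itself, and a major complication from early OWSV halts the study. Much of this stands. What remains exposed is a complication that is non-major, or not attributed to the valve, and that takes the patient out before the Session 2 list is completed. The halt rule does not close that gap: 'major' is undefined, and halting is not a rule for counting the patient.

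It can also be said that the arms are not cleanly separated. Section 4f could cover a control whose deterioration prevents the planned Session 2 trial, and the cuff-deflation and discharge rules reach both arms. This stands. The imbalance is likely, not certain, and equal fractions in both arms (fI = fC and gI = gC) leave the odds ratio unchanged.

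A reader might infer more than the documents support:

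- That data already collected are discarded. No passage says so, and the codebook cited in section 7b is not supplied.
- That bias in Hypothesis 3b is established. Its direction depends on g as well as f.
- That equal removal always shrinks the risk difference. At 90% v 70% with half of complicated patients removed in each arm, the arms show 0.45/0.55 = 81.8% v 0.35/0.65 = 53.8%, so the difference rises from 20 to 28 points.
- That Hypothesis 3a is biased. This is only possible, since nothing indicates how removed patients would have scored.

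**Conclusion.** The concern holds in this form. The plan has an explicit rule that ends study participation after a clinical change, bars return, and makes no provision for follow-up or analysis by assigned arm. If followed, it can bias the safety comparison in Hypothesis 3b towards no difference or towards early OWSV. This requires that patients with complications are removed more often than those without, and more so in the intervention arm.

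The size is unknown. Under the assumptions stated above, a true excess of 10 points is seen as 8.4, 5.8 or 1.1 points when 10%, 25% or 50% of complicated intervention patients are removed. At the low end the effect is small; at the high end the excess nearly disappears. Because the rule touches the trial's stated purpose and is cheap to change, it should be fixed before analysis.

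**What to change.** - Reword 4f, 4g and 7d so that stopping or deferring the valve does not end study participation, and only withdrawal of consent ends data collection. Clinical decisions about the valve stay as they are.
- State that all randomised patients are analysed in their assigned arm.
- For Hypothesis 3b, count the five listed complications from randomisation to the Session 2 post-assessment (48-60 hours) for every randomised patient, including any that led to stopping. Use the bedside assessment or, if it is missed, the electronic record. Report later complications separately: both arms are scheduled for valve trials from Session 2, so a count over the full 4 weeks would dilute the early-versus-standard contrast.
- Take ICU stay and mortality from the record for all randomised patients, and attempt the Session 2 QOL-MV in those who stopped the valve.
- Report stops and withdrawals by arm, timing (before or after Session 2) and reason.
- Reconcile 'removed', 'dropped', 'discontinued' and 'deferred' across sections 4f, 4g, 7d and 8b.

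The cost is three reworded paragraphs, a sentence defining the analysis set, one table, and some extra chart review for at most 50 patients in records the team already uses. The main drawback is that complications taken from the record may not match bedside findings exactly, so the source of each should be noted.

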## 5. Inclusion/Exclusion Criteria

### Inclusion Criteria:

- Patient who received a percutaneous tracheostomy
- Glasgow Coma Scale score  $\geq 9$
- Confusion Assessment Method –ICU (CAM-ICU): negative
- Richmond Agitation Sedation Scale (RASS): -1 to +1
- Able to understand English

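### Could patients be randomised before their CAM-ICU status is known, because step A of the sequence lists only GCS and RASS?

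*Combined protocol and SAP*

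**What the plan says.** Section 5 lists five inclusion criteria, one of which is "Confusion Assessment Method –ICU (CAM-ICU): negative".

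The sequence in section 4.a then runs in lettered steps:

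- Step A: "Screening by Tracheostomy Nurse Practitioner following percutaneous tracheotomy". Two scales are listed under it, GCS and RASS.
- Step B: "Speech-Language Pathologist consult is placed for patients meeting study inclusion criteria".
- Step C: "Patient consent is obtained by Tracheostomy Nurse Practitioner or Speech-Language Pathologist".
- Step D: "Randomization into Intervention and Control groups".
- Step E: "Session 1 within 12-24 hours following percutaneous tracheotomy". Both groups have a pre-assessment that includes CAM-ICU.
- Step F: Session 2, at 48-60 hours. Both groups have a post-assessment that again includes CAM-ICU.

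Section 8.b adds that the tracheostomy nurse practitioner screens patients for inclusion, without listing instruments.

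Three places deal with removal or deferral. Sections 4.f and 4.g cover a clinical change that rules out continuing with the valve, and 4.f adds hospital discharge. Section 7.d covers a change that rules out deflating the cuff. Section 8.b covers the speech-language pathologist's judgement that the patient is not yet a candidate. None names CAM-ICU.

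**The concern.** CAM-ICU is the only inclusion criterion whose named appearances in the schedule all come after randomisation. GCS and RASS, the two other bedside scales among the criteria, are both listed at step A. A reader who takes step A as the complete screening battery would conclude that a patient could be consented and randomised, and only then be found not to meet an entry criterion.

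Someone would then have to decide whether to keep that patient. Patients are not blinded (section 4.c), no blinding of staff is described, and no rule is written for a positive result. At Session 1 the intervention group has a speech-language pathology evaluation and a possible valve trial, while the control group has neither. Informal removal could therefore operate in one arm and not the other. Exclusions after allocation that differ by arm can bias the comparison on speech intelligibility and quality of life, and in a pilot of 25 per arm each one counts.

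**Working it through.** The plan gives no figure on this point to reproduce, so the check sets the texts side by side.

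**Where each inclusion criterion appears in the sequence**

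| Criterion (section 5) | Where section 4.a names it | Relative to step D |
|---|---|---|
| Percutaneous tracheostomy | Opening line of step A | Before |
| GCS | Step A, item 1 | Before |
| RASS | Step A, item 2 | Before |
| CAM-ICU negative | Sessions 1 and 2 only | After |
| Understands English | Nowhere | Not named |

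So 1 of 5 criteria is named only after randomisation, and 2 of 2 scheduled CAM-ICU tests follow step D. The factual observation is right.

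**Is step A a full list of what is checked?** No. It omits one other inclusion criterion (English) and all seven exclusion criteria. If absence from step A meant that an item was not checked before randomisation, none of the exclusions would be checked either. That reading cannot be intended.

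**What does step B require?** It restricts the consult to patients who meet the inclusion criteria. A negative CAM-ICU is one of them. Steps C and D come after B, so CAM-ICU status must be known before either. Section 8.b agrees. What the text leaves out is the source: a test by the nurse practitioner, or a result already in the ICU record.

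**Why test again at Session 1?** Sessions 1 and 2 are the pre- and post-assessments for both arms. CAM-ICU sits there beside SOFA and the quality-of-life survey, as a study measure. Measuring it at baseline does not show that it was left out of screening.

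**Does the absence of CAM-ICU from the removal rules signal a gap?** Of the three places with such rules, 0 mention CAM-ICU, but 0 mention GCS or RASS either. The plan uses these scales as entry criteria and not as conditions for staying in. A positive result that triggers none of the stated reasons leaves the patient in the study; confusion that prevents the valve trial already falls under section 4.f.

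**Size.** One patient is 1/25 = 4% of an arm. The documents give no CAM-ICU-positive rate. Purely as an assumption, let a share p of the 50 be positive at Session 1 and all be excluded evenly, which the plan does not call for. With assumed two-sided 5% significance and 80% power, the detectable standardised difference is (1.960 + 0.842) × √(2/n), where n = 25 × (1 − p):

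| p | Excluded (50p) | n per arm | Detectable difference |
|---|---|---|---|
| 0 | 0 | 25 | 0.79 |
| 0.10 | 5 | 22.5 | 0.84 |
| 0.20 | 10 | 20 | 0.89 |
| 0.30 | 15 | 17.5 | 0.95 |

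These figures show what mass exclusion would cost. They are not evidence that it would happen.

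**The case for a change.** The strongest case for a change is that an implied check has no stated time or source. Step B relies on a result that no earlier step produces, and the Session 1 list shows CAM-ICU as an item separate from the electronic records, which does not suggest that a chart value is meant. On handling, the statistical plan in section 7.c is silent on patients found ineligible after randomisation, and the general removal rules can act at Session 1 only where a valve trial is attempted, that is, in the intervention arm. Adding CAM-ICU to step A and one sentence on analysis would cost little.

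Part of this stands: the sequence does not name the check, and the analysis text has no explicit sentence. Neither point shows an ineligible patient being randomised, since that would breach step B. The asymmetry at Session 1 comes from tying removal to feasibility of the valve trial; it would apply to any clinical change, and naming CAM-ICU at step A would not alter it. For a control patient at Session 1, the lack of any trigger points to retention, which is also what the suggested analysis sentence would say. The added text would mostly write down what the plan already implies.

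**Conclusion.** No change is called for. The observation about step A is accurate, but it is a drafting gap in a list that is visibly incomplete. The requirement itself is in place: the inclusion criteria, CAM-ICU among them, must be met before consent and randomisation. The Session 1 and 2 tests serve as before-and-after measures, and a later positive result is not by itself a stated reason to remove anyone.

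The size is unknown from the documents and has no demonstrated floor above zero; the only firm figure is 4% of an arm per patient lost. The conclusion assumes that staff apply step B as written and that analysts keep randomised patients unless a stated removal reason applies. If the trial's records showed patients allocated without a prior CAM-ICU result, or removed because of a later positive one, that would be a question of conduct to raise then.

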### Exclusion Criteria:

- Open tracheostomy
- Laryngectomy
- Presently using OWSV or capped trach
- Foam-filled cuffed tracheostomy tube
- Presence of known severe airway obstruction
- Presence of post-operative bleeding requiring transfusion or packing
- Presence of air-leak around the cuff resulting in respiratory decompensation

## 6. Drugs/ Substances/ Devices

- a. The rationale for choosing the drug and dose or for choosing the device to be used.

We are not studying the efficacy of the one-way speaking valves. We know that they work. We are studying the timing of when to start using OWSV.

- b. Justification and safety information if FDA approved drugs will be administered for non-FDA approved indications or if doses or routes of administration or participant populations are changed.

N/A

Date: 2/06/18

Principal Investigator: [name]

Application Number: **IRB00080981**

- c. Justification and safety information if non-FDA approved drugs without an IND will be administered.

N/A

## 7. Study Statistics

- a. Primary outcome variable.

Speech intelligibility

- b. Secondary outcome variables.

- Patient characteristics
- Quality of Life
- Complications
- Time to events
- Length of stay
- Mortality

\*See codebook for list of additional variables

- c. Statistical plan including sample size justification and interim data analysis.

Mean, standard deviation, median and inter-quartile range will be calculated for continuous variables. Paired t-tests will be used to compare pre and post assessment scores for continuous variables. Frequencies and percentages will be calculated for categorical variables. Chi square and Fisher Exact tests will be used to compare pre and post assessment scores of categorical variables. Sample size is estimated based on 30% of tracheostomy patients who might be awake and interactive at the Johns Hopkins Hospital in 2016, as per the tracheostomy database. According to the 2014 data, we found that about 55 patients were awake and interactive while having a percutaneous tracheostomy tube at the hospital. Considering a 10% of the patients who may not be interested in the study, we will plan for a sample size of 50 with 25 in the intervention group and 25 in the control group.

- d. Early stopping rules.

If patients have changes in clinical condition that prevents cuff deflation, they will be dropped from the study. The study will be halted if any major complications occur from early trial of OWSV.

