### 1. Abstract

- a. Provide no more than a one page research abstract briefly stating the problem, the research hypothesis, and the importance of the research.

Over the past several decades, age-adjusted, population-based rates of tracheostomy has doubled (Mehta, Syeda, Bajpayee, Cooke, Walkey & Wiener, 2015). Acutely ill patients with tracheostomy have reported that the ability to speak is fundamental to social communication and to their personal identities, and conversely, the lack of voice often leads to frustration and feelings of confinement (Carroll, 2007; Foster, 2010). The use of one-way speaking valves (OWSV) is supported in the literature as a way to restore speech in patients with tracheostomy who are on or off of mechanical ventilation (Hess, 2005). The benefits of speech restoration and the consequences of its delay suggest that the early use of OWSV in patients with tracheostomy may be beneficial. However, the literature lacks clear evidence for the optimal timing to initiate the use of OWSV or its clinical outcomes.

The timing for initiating OWSV use varies internationally, and the timing most appropriate for specific patient populations is unknown. In the United States, evaluation for speech using an OWSV has traditionally been at least 48 hours following tracheostomy procedure. On the other hand, speech language pathologists (SLPs) in Europe and Australia indicated (personal communication) that they initiate OWSV evaluation as early as 4 hours after the tracheostomy procedure. Furthermore, the safety of early use of OWSV may be related to the type of tracheostomy procedure itself. A representative from Passy-Muir, the manufacturer of OWSV, stated in an interview that the 48 hour waiting period in the United States is based on traditional open surgical tracheostomy, rather than the percutaneous procedure. Notably, percutaneous tracheotomy has been shown to be associated with a lower overall postoperative complication rate when compared with open operative tracheotomy, and the use of percutaneous technique is on the rise (Freeman, Isabella, Lin, & Buchman, 2000).

Therefore, we propose a prospective randomized clinical trial - pilot study to investigate the safety of early use of OWSV in patients undergoing a percutaneous tracheostomy.

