#### **Specific Aim 2: Determine the effect of the early use of the OWSV on the quality of speech.**

Hypothesis 2a: The increase in the speech intelligibility scores from pre- to post- assessment will be significantly higher in the patients who receive early OWSV compared to those who receive it the traditional way 48 hours after undergoing a tracheostomy.

Research Question 2b: Is the duration of speech longer for patients who start using OWSV earlier compared to those who start late?

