#### **Specific Aim 3: Determine the effect of early use of the OWSV on clinical outcomes.**

Hypothesis 3a: The increase in the health-related quality of life scores from pre- to post- assessment will be significantly higher in the patients who receive early OWSV compared to those who receive it the traditional way 48 hours after undergoing a tracheostomy.

Hypothesis 3b: There will be no significant changes in the rate of complications between patients receiving early versus standard use of the OWSV.

Hypothesis 3c: Patients who begin to use the OWSV early will have a significantly shorter lengths of stay in the ICU than patients who start using OWSV after 48 hours.

**3. Background** (briefly describe pre-clinical and clinical data, current experience with procedures, drug or device, and any other relevant information to justify the research)

Current standard of care to wait 48 hours following tracheostomy procedure to initiate OWSV assessment and treatment, however, there is scant evidence in the literature justifying this amount of time. 201 patients out 272 patients who received a tracheostomy received SLP consult for in 2014. Based on prior data from the tracheostomy database 30% of mechanically ventilated and / or tracheotomized patients tend to be awake and interactive, and attempt to communicate.

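### The abstract's purpose is safety, but the only primary outcome is speech intelligibility, and the secondary complication hypothesis cannot show safety at 25 per arm

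*Combined protocol and SAP*

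**What the plan says.** Section 1 (Abstract) ends by proposing a randomised "pilot study to investigate the safety of early use of OWSV in patients undergoing a percutaneous tracheostomy". It gives no other purpose in that sentence.

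Section 2 lists three aims. Specific Aim 2 is to "Determine the effect of the early use of the OWSV on the quality of speech", and Hypothesis 2a compares the change in intelligibility between early and standard timing. Safety appears under Specific Aim 3 as Hypothesis 3b: "There will be no significant changes in the rate of complications between patients receiving early versus standard use of the OWSV". No margin is attached to it.

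Section 7a gives one primary outcome, "Speech intelligibility". Section 7b lists "Complications" as one of six secondary items. Section 7c sets the sample at 50, 25 per arm, from the number of suitable patients and an allowance for refusal. Section 7d adds a safety rule: "The study will be halted if any major complications occur from early trial of OWSV".

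Section 4a has both arms checked for the same five complications at Session 1 (12 to 24 hours after the procedure) and Session 2 (48 to 60 hours).

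**The concern.** A trial announced as a safety study will be judged on its primary outcome, and here that outcome carries no information on safety. What the plan says about safety rests on a hypothesis of no significant difference, tested in a sample that was not chosen for that purpose. In a small trial such a hypothesis is easily left standing, because a test with little power is usually non-significant whatever the truth.

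Two misreadings are then open. A favourable intelligibility result from a trial introduced as a safety study could be taken to support the safety of early use. A non-significant complication test could be taken to confirm Hypothesis 3b. The plan's text does not rule out either one.

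**Working it through.** **1. The plan's own figure.** Section 7c gives about 55 suitable patients (2014 data) and 10% refusal: 55 × (1 − 0.10) = 49.5, which rounds to the stated 50. The figure reproduces. It is a count of available patients and uses no effect size, standard deviation, complication rate, margin, alpha or power. It is therefore tied to neither intelligibility nor complications.

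**2. Purpose against outcome.** The abstract's purpose is safety. The primary outcome is a speech score, which matches Aim 2. The safety hypothesis is 3b, and its outcome is secondary. The mismatch between abstract and Section 7a is textual and needs no assumption. The remaining steps ask whether the secondary safety outcome can fill the gap.

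**3. What 25 early-arm patients can say.** Exact (Clopper-Pearson) two-sided 95% upper limits:
- 0/25: 1 − 0.025^(1/25) = 0.137, or 13.7%.
- 1/25: the p that solves (1 − p)^25 + 25p(1 − p)^24 = 0.025, which is 20.4%.
- If only 20 were evaluable (my assumption, for illustration), 0/20 gives 1 − 0.025^(1/20) = 16.8%.

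The chance of seeing at least one event in 25 is 1 − (1 − p)^25: 40% for a true rate of 2% and 72% for 5%.

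**4. What a non-significant comparison can say.** The documents give no complication rates, and Section 7c describes its categorical tests as comparisons of pre with post. I therefore assume a two-sided Fisher exact test between arms at 0.05. Exact power at 25 per arm, by assumed rates:

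| Rates in the two arms | Power |
|---|---|
| 5% and 15% | 7% |
| 5% and 20% | 20% |
| 10% and 30% | 31% |
| 10% and 40% | 59% |

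An observed split of 5/25 against 0/25 gives p = 2 × C(25,5)/C(50,5) = 2 × 53,130/2,118,760 = 0.0502, still non-significant.

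**5. What a margin would require.** For non-inferiority with equal true rates p, margin m, one-sided 0.025 and 80% power, n per arm = (1.960 + 0.842)² × 2p(1 − p)/m². For p of 5%, 10% and 20%, a 10-point margin needs 75, 142 and 252 per arm. A 20-point margin needs 19, 36 and 63. With 25 per arm, only the widest margin at the lowest rate is within reach. These rates and margins are assumptions.

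**6. What the listed checks compare.** In Section 4a, Session 2, the complication check is part of the post-assessment, which is listed before the control arm's first valve trial. Session 3 lists no complication check. The interval from Session 1 to Session 2 therefore compares early valve use with no valve yet, not with standard use as Hypothesis 3b words it.

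**The case against.** The strongest reply is that the plan is more coherent than the abstract's last sentence suggests. Section 2 is the place for objectives, and intelligibility serves one of its three aims. The abstract itself opens with loss of voice and says evidence on timing is lacking. Which aim a pilot ranks first is the sponsor's choice. All of this stands. It explains the choice of primary outcome but leaves the abstract's purpose unmatched.

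A reader might infer that Section 6a makes matters worse, because it says "We are not studying the efficacy of the one-way speaking valves". The documents do not support that. The passage goes on to say "We are studying the timing of when to start using OWSV", and comparing intelligibility by start time is a timing question.

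A reader might also infer that safety is ignored. It is not. There is Hypothesis 3b, a check of five complications in both arms at two sessions, monitoring during valve trials, and a halting rule. That rule, however, does not define which complications count as major, and it gives no estimate of risk.

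Finally, a reader might conclude that complications must become the primary outcome. That does not follow. With 0/25 still allowing 13.7%, a primary safety outcome would not establish safety either. It would also need a defined event list and window. Air trapping, named as a risk in Section 8a, is recorded only during valve trials and is not in the shared list. Patients whose condition changes are removed under Sections 4f and 7d, so a count over all randomised patients needs recording after removal.

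**Conclusion.** The point holds in a limited form. The abstract's safety purpose is reflected neither in the primary outcome nor in the sample size. Hypothesis 3b cannot make up for this: it has no margin, and at 25 per arm a non-significant result is compatible with large differences in complication rates. If all 25 early-arm patients are evaluable, no events still leaves an upper limit of 13.7%, and one event leaves 20.4%. Removals would widen these limits.

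The mismatch rests on the text alone. The two limits rest on complete evaluability. The power and non-inferiority figures rest on assumed rates, margins and tests, and serve only to show scale. Making complications primary or co-primary is open to the sponsor but is not a required correction.

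**What to change.** 1. Reword the purpose in the abstract to match Section 2 and Section 7a: the effect of early versus standard timing on speech, with safety described as preliminary.
2. For Hypothesis 3b, report for each arm the proportion of patients with at least one new listed complication between the Session 1 and Session 2 assessments, and the between-arm difference, all with exact 95% confidence intervals.
3. State that neither the intelligibility result nor a non-significant complication comparison will be taken as evidence that early use is safe.
4. State that this window ends before the control arm's first valve trial, so the contrast is early valve against no valve yet.
5. State that complications will also be recorded through Session 2 in patients removed from the study.

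Items 1 to 4 are wording and analysis of data already planned. Item 5 asks for some follow-up that the removal rules do not now provide. The main cost is that the trial gives up any firm safety claim. If the sponsor prefers a primary or co-primary complication outcome, its events, window and denominator must be defined, and a precision target or margin stated.
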